Patients must have clinical diagnosis of chronic low back pain. Pain must be present on most days for at least 6 months. The pain must be either restricted to low back or associated with radiation to the proximal portion of the lower limb only (Class 1 and 2 per Quebec Task Force on Spinal Disorders). Study candidates must not have: a) neurological radicular signs; b) presumptive compression of a spinal nerve root on a simple radiogram (that is, spinal instability or fracture); or c) compression of a spinal nerve root confirmed by specific imaging techniques (computerized tomography [CT], myelography, or magnetic resonance imaging [MRI]) or other diagnostic techniques (for example, electromyography). The above diagnosis shall be made by a study physician and will be based on history, and physical and neurological examination. In addition, absence of spinal fracture, spondyloisthesis grade 3 or 4, tumor, abscess or acute pathology in the low back/abdominal regional must be confirmed by historical record of imaging studies (any of the following: plain x-ray, CT, or MRI). As per the study physician's opinion, there must be no clinically significant change in the condition since the time of imaging. A study physician will review medical charts and interview patients to determine disease criteria.

Pregnenolone: Pregnenolone is available over-the-counter and sold as a dietary supplement in the U.S., and estimated to be used by thousands of people. It has a very favorable side effect profile among clinical studies conducted to date; please see Appendix 3 for recent pregnenolone safety data summary. Despite its ubiquitous availability as a dietary supplement, pharmacokinetic data for pregnenolone are limited. Please see also summary of pregnenolone in the PDR for Nutritional Supplements (attached). No serious adverse events have been attributed to pregnenolone to date.

Treatment Compliance

Compliance for each visit interval is defined as taking between 80% and 120% of the study drug prescribed for that interval. For subjects who demonstrate noncompliance, the PI and/or study coordinator will counsel patients on the importance of study drug compliance and drug accountability. Patients who miss more than 6 consecutive doses of medication or are less than 80% compliant will be withdrawn from the study.

The following procedures will be employed to assure appropriate drug accountability:

- Drug accountability will be emphasized at the screening visit and throughout the trial.
- Drug accountability forms will be provided in the clinical trial records binder or similar file.
- Drug accountability will be monitored throughout the study.

Each patient will be instructed to return all study drug packaging and unused at each visit. Records will be kept of all drug dispensed to and returned by the subjects throughout the study.

CONSENT PROCESS

As outlined above, we are requesting a waiver of Informed Consent and HIPAA Authorization to identify and contact Veterans and MIRECC Repository participants who may be eligible for the study. A subject who is judged likely to meet all of the inclusion criteria and none of the exclusion criteria will meet with a member of the research team to discuss the research protocol, and to determine if the patient is capable of providing informed consent. This study utilizes an informed consent form. The subject will be provided with a

description (verbal and written) of the informed consent form, which includes the risks along with procedures to minimize these risks, and the subjects' rights and responsibilities. Subjects will be given the opportunity to read the consent form and ask questions. Subjects will be assured that participation in this research study is voluntary and that they may withdraw from the study at any time without adversely affecting their medical care or any benefits they might be receiving. They may also refuse to answer any research questions during interviews. Subjects who are eligible for the study and choose to participate will sign the consent form in the presence of a member of the research team and a witness.

STUDY INTERVENTIONS

Primary Outcome Measures

- The primary efficacy outcome measure will be the weekly mean of the 24-hour average pain severity scores recorded daily on an 11-point Likert scale, an ordinal scale ranging from 0 (no pain) to 10 (worst possible pain). Patients will be asked to complete their pain diary at bed time.

Secondary Outcome Measures

- The first secondary outcome measure will be the Brief Pain Inventory (BPI) (Severity and Interference scores). The BPI is a self-reported scale that measures the severity of pain and the interference of pain on function. The scores range from 0 (no pain) to 10 (pain as severe as you can imagine). There are 4 questions assessing worst pain, least pain, average pain in the past 24 hours, and the pain right now (As described above average pain scores will be used in the primary outcome measure). The Interference scores range from 0 (does not interfere) to 10 (completely interferes). There are 7 questions assessing the interference of pain in the past 24 hours for general activity, mood, walking ability, normal work, relations with other people, sleep, and enjoyment of life. Questions from the BPI will be asked at each patient visit.
 - The Tower of London is a clinician administered subtest from the BAC-A which measures executive functioning.
 - Digit Sequencing Task is a clinician administered subtest from the BAC-A which measures working memory.
 - The Davidson Trauma scale is a self-report questionnaire that measures trauma symptoms.

Routine laboratory assessments will be completed at each visit (CBC, Chem 7, GI panel) and will require the patient to donate approximately 10ml of blood. Additional blood samples will be collected for serum analysis during all study visits. Serum samples will be frozen in a -80 degree freezer. Upon completion of the study, samples will be thawed and analyzed using Gas Chromatography/Mass Spectrometry. Patients will receive an ECG at Visit 1 and the final study visit. Vital signs will be assessed and recorded at each study visit.

Additional assessment measure descriptions are listed below.

Study Timeline:

1. Referred patients and patients responding to IRB-approved advertisements or IRB-approved recruitment letters, phone calls (with IRB-approved phone script), will meet with a member of the research team to discuss the study and the risks and benefits of participation. In addition, patients will be screened for exclusion and inclusion criteria. If subjects are interested, the informed consent document will be discussed with them. Patients will have the option of taking the informed consent with them and discussing the matter with family, friends or clinicians. If the patient is followed by a psychiatrist, the psychiatrist will be consulted prior to randomization regarding the patient's appropriateness for enrollment in the study.

2. Once the informed consent is signed, the subject will proceed to the initial screening procedures. First, patients will receive a more detailed assessment than what was queried on the telephone pre-screening interview to determine whether they meet qualifications to participate in the study.
3. We will then determine whether subjects are in good health. A research physician will examine patients before starting the study. Patients will have a venous puncture for laboratory testing (please see Schedule of Events). Subjects will receive an ECG at Visits #1 and #6. Since patients may be on antidepressant and occasionally on antipsychotic medicines (treatment-as-usual), it is part of routine clinical care to receive an ECG at least once each year on these agents. A follow-up ECG at Visit #6 will be performed to confirm that there are no changes in ECG tracings (since there is one report of palpitations in the existing scientific literature following pregnenolone). Patients with significant abnormal physical exam, blood tests, or ECG will be excluded from the study and referred to their primary care provider.

Table 1. Study Schedule

Visit	1	2	3	4	5	6	Follow Up	Follow Up
	Screen	Baseline					Phone	Phone
Week	0	1	2	3	4	6	7	8
Inclusion/Exclusion (5 min)	X							
Informed Consent (15 min)	X							
Demographics (10 min)	X							
Medical History (10 min)	X							
Psychiatric Diagnosis (MINI) (15 min)	X							
Physical Exam and ECG (30 min)	X						X	
Vital Signs (5 min)	X	X	X	X	X	X		
Urine Collection: (5 min)								
Drug Screen	X	X		X			X	
Urinalysis	X	X	X	X	X	X		
Urine Pregnancy Test (females only)	X	X	X	X	X	X		
Concomitant Medications (5 min)	X	X	X	X	X	X		
Patient Pain Diary (5 min)	X	X	X	X	X	X		
Adverse Events (5 min)		X	X	X	X	X	X	X
Brief Pain Inventory (10 min)	X	X	X	X	X	X		
Patient's Global Impressions of Improvement (2 min)			X	X	X	X		
Fagerstrom Test for Nicotine Dependence (2 min)	X	X					X	
Beck Depression Inventory (5 min)	X	X	X	X	X	X		
Davidson Trauma Scale (7 min)	X	X	X	X	X	X		
Athens Insomnia Scale (5 min)	X	X	X	X	X	X		
Roland Morris Scale (5 min)	X	X					X	
BAC-A subtests (Tower of London and Digit Sequencing Task) (10 min)	X	X	X	X	X	X		
Connor Davidson Resilience Scale (5 min)	X	X	X	X	X	X		
36-item Short-Form Health Survey (5 min)	X	X	X	X	X	X		
Columbia Suicide Severity Rating Scale (5 min)	X	X	X	X	X	X	X	X
BLOOD DRAW (15 minutes)								
Blood draw (Pax Gene tube)	X							
Blood draw (2 purple top tubes)	X							
Blood draw (neurosteroids)	X	X	X	X	X	X		
Blood draw (TSH, prolactin)	X						X	
Blood draw (Chem 7, GI Panel, CBC)	X	X	X	X	X	X		
Dispense Drug or Placebo	N/A; Diary start	Placebo	Placebo or 50 mg Preg BID	Placebo or 150 mg Preg BID	Placebo or 250 mg Preg BID	N/A; taper begins	N/A; follow up phone call	N/A; follow up phone call
Total Time Commitment	179	99	94	94	94	126	10	10

4. Following the screening process, patients will begin a one-week period in which they will record pain levels in a daily diary (Visit #1). The following week (Visit #2), they will begin a one-week placebo-only lead-in period. On the days that patients are given study medication, a set of vital signs will be assessed including pulse, blood pressure, respiratory rate, temperature, and weight. Female participants will be asked to provide a urine specimen for a urine pregnancy test at point of care, during each study visit. With the study medication, the patients will be told that they could be getting placebo (a sugar pill) or active compound.

They will be asked to take the medication twice a day; once in the morning and once at night. The initial dose at Visit #2 will always be placebo (one-week placebo single-blind lead-in phase).

5. Subjects will return for a study visit every week (except for Week 5). Vital signs will be assessed at each visit. A member of the research team will ask subjects about possible side effects and adverse reactions (Adverse Event Form). Patients will be asked to return capsules of pregnenolone or placebo to determine compliance with study medication. The subject will then be given a new supply of capsules (either pregnenolone or placebo, depending upon random assignment) at Visits #3, #4, and #5. At baseline (Visit #1) and at the final visit (Visit #6), patients will receive a Chem 7, GI panel, CBC, TSH, prolactin, lipid panel, urine drug screen, and urinalysis; all patients will receive urinalysis and female patients will also receive a pregnancy test at all visits. Urine drug screens will be administered at Visits 1, 2, 4 and 6. A Chem 7, GI panel, and CBC will also be performed at Visits #2,3,4, and 5 (a Chem 7, GI panel, and CBC will therefore be performed at each study visit).
6. At Visits #1, 2, 3, 4, 5 and 6, three extra red-top tubes will be collected for determination of pregnenolone levels and pregnenolone metabolite levels. Serum will also be utilized for protein and other small molecule characterizations. At the end of these analyses, any remaining serum will be destroyed.
7. At Visit #1, two purple-top tubes and one PAX gene tube (blood RNA tube) will be collected for genetic analyses examining polymorphisms in the enzymes leading to neurosteroid synthesis and metabolism, as well as other candidate genes relevant to pathophysiology and treatment.
8. At Visit #6, patients will be instructed to taper the study medication by 100mg/day (for example, if the patient is taking 500mg of pregnenolone at Visit #6, the following day he will take 400 mg, the day after 300mg, etc. until the taper is complete).
9. At the final visit (Visit #6), patients will receive psychiatric assessments, vital signs, and side effect assessment. In addition, the physical exam and ECG will be repeated.
10. BPI, BDI, DTS, AIS, 36-item Short form Health Survey, selected BAC-A subtests, CDRS and CSSRS will be administered during each study visit. The Patient's Global Impressions of Improvement will be administered during Visits #3, #4, #5 and #6. The Roland Morris Scale and Fagerstrom Test for Nicotine Dependence (FTND) will be administered at Visit #1, #2 and #6. Please see schedule of events.
11. All subjects who complete the entire study (6 visits total) will receive two follow-up phone calls during Weeks #7 and #8 and be asked about adverse events (Hillside Adverse Events) and suicidality (CSSRS).

ADVERSE EVENTS AND SAFETY EVALUATIONS

Adverse Events: Adverse events will be recorded by administration of the Hillside Adverse Event Form and reviewed by a study physician (please see physician study team schedule/cascade). Adverse events will be assessed at all study visits after the screening visit (i.e. Visits 2-6). In addition, adverse events will be assessed by a follow-up telephone call at the end of the study medication taper (Week 7) and again one week after study medication has been stopped (Week 8). In addition to receiving these regular adverse effect assessments, patients will be given a toll free study number that they can call if they have questions regarding the dose escalation schedule or medication side effects. They will also be provided with the cell phone number of the study PI, [name], PhD as well as [name], MD. Other covering VA physicians (as part of the call cascade) will be accessible to [name] as per the call schedule.

Suicidality Safety Procedures for Follow-Up Phone Calls:

If a participant reports suicidality (suicidal ideation, gesture, or attempt) as per the Columbia Suicide Severity Rating (CSSRS, which is an FDA-recommended assessment for suicidality in clinical trials) during any follow-up phone call, a study physician will be notified immediately to determine whether the situation requires immediate clinical intervention. If a participant is thought to be at imminent risk to self, he/she will be referred immediately to emergency psychiatric care at the Durham VA Emergency Department, to Psychiatric

Emergency Services (PEC) at the Durham VA, or to the participant's local Emergency Department for further evaluation. If the participant is unwilling or unable to get to emergency psychiatric care and appears to be in imminent danger of self-harm, the study team will contact local law enforcement who will follow up with the participant at their current location.

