Experimental Design: The proposed design is a randomized, double-blind, two-arm trial of pregnenolone and placebo to determine the possible analgesic effects in OEF/OIF Veterans with chronic low back pain. The total study duration is 8 weeks (6 study visits followed by two-follow up phone calls). All patients will monitor pain symptoms for one week with pain diaries, followed by a 1-week placebo-only lead-in period, 90 subjects will be randomly assigned to one of two groups. Of these subjects, 45 subjects will receive pregnenolone, and 45 subjects will receive placebo for 4 weeks (in addition to the taper period of 5 days). Patient interview assessments and laboratory studies will be performed at each interview time point. Pregnenolone, allopregnanolone and other neurosteroid metabolites will be determined by gas chromatography / mass spectrometry (GC/MS), proceeded by high performance liquid chromatography (HPLC). Those subjects randomized to pregnenolone will receive this neurosteroid on the following schedule:

- Pain symptom monitoring with pain diaries for 1 week, then
- Placebo lead-in phase 0 mg in two doses (0 mg, PO, BID) for 1 week, then
- Pregnenolone 100 mg in divided doses (50 mg, PO, BID) for 1 week, then
- Pregnenolone 300 mg in divided doses (150 mg, PO, BID) for 1 week, then
- Pregnenolone 500 mg in divided doses (250 mg, PO, BID) for 2 weeks.

Dosing: Pregnenolone fixed escalating up to 500mg/day will consist of the following schedule:

Visit 1 (week 0, screening visit) and pain symptom assessment

Visit 2 (week 1) placebo lead-in (all participants)

Visit 3 (week 2, baseline visit): 50mg PO, BID x 1 week,

Visit 4 (week 3): 150mg PO, BID x 1 week,

Visit 5 (week 4): 250mg PO, BID for two weeks.

Visit 6 (week 6): No medication will be dispensed; study medication will be tapered by 100mg per day and then discontinued. The FDA has reviewed this protocol and issued an Investigational New Drug number (IND #114,799) for this randomized controlled trial utilizing the pregnenolone doses above for low back pain, and has provided a formal permission to proceed letter for this study. In addition, [name] (the PI's primary mentor on this VA funded Career Development Award) currently holds FDA IND numbers for the use of pregnenolone for treatment of schizophrenia (IND #71,768), PTSD (IND #73,099) and TBI (IND #78,270).

Methodology for Neurosteroid Identification and Quantification:

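### The protocol specifies a taper after Visit 6 but names no source of drug for it, and its dispensing and return rules do not fit the taper

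*Combined protocol and SAP*

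**What the plan says.** **Taper.** In Research Design and Methods, the Experimental Design paragraph gives four weeks of assigned treatment "in addition to the taper period of 5 days". The Dosing list gives the Visit 6 entry as "No medication will be dispensed; study medication will be tapered by 100mg per day and then discontinued". Study Timeline item 8 says "At Visit #6, patients will be instructed to taper the study medication by 100mg/day", with the example that a patient on 500 mg steps down so that "the following day he will take 400 mg, the day after 300mg, etc. until the taper is complete".

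**Supply.** The last dosing entry before the taper is "Visit 5 (week 4): 250mg PO, BID for two weeks". Study Timeline item 5 says that the subject is "given a new supply of capsules (either pregnenolone or placebo, depending upon random assignment) at Visits #3, #4, and #5". In Table 1 the dispensing row for Visit 6 shows nothing issued and marks the start of the taper.

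**Return.** The accountability list under Treatment Compliance says "Each patient will be instructed to return all study drug packaging and unused at each visit". A noun is missing after the word unused; drug is the natural reading. Study Timeline item 5 also asks for capsules back so that compliance can be determined. Neither place exempts Visit 6 or says that counted capsules are handed back.

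**Follow-up.** Adverse Events and Safety Evaluations describes the planned contact as "follow-up telephone call at the end of the study medication taper (Week 7) and again one week after study medication has been stopped (Week 8"). Study Timeline item 11 places the two calls during Weeks 7 and 8. They collect adverse events and suicidality.

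**The concern.** Each rule is reasonable alone. Together they require a patient to take drug after Visit 6 that no passage supplies and that the return rule, read literally, would collect. The study team would have to choose between an abrupt stop from the highest dose, where the protocol itself states a taper, and an improvised supply. If practice varied, some patients would be tapered and others not. I found no item in Table 1 or the Study Timeline that records the date of last dose, so the two groups could not be reliably separated afterwards.

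What is at stake is the reading of the only data collected after Visit 6, the adverse-event and suicidality reports from the two calls. Their meaning depends on when and how drug was stopped.

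**Working it through.** **Inputs.** Daily dose at Visit 6: 500 mg (250 mg twice daily, Dosing). Step: 100 mg per day (Dosing; Study Timeline item 8). Visit 5 to Visit 6: week 4 to week 6, 14 days (Dosing; Table 1). Stated taper length: 5 days (Experimental Design). Compliance range: 80% to 120% of the drug prescribed for the interval (Treatment Compliance).

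**1. The plan's own taper length.** The daily dose after k steps is 500 − 100k, which gives 400, 300, 200, 100 and 0 mg. That is five daily steps, four of them with drug. The stated 5 days is reproduced if the day of reaching zero is counted.

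**2. Drug the taper needs.** 400 + 300 + 200 + 100 = 1,000 mg, equal to two days at full dose. A patient at a lower dose at Visit 6 would need less; from 300 mg per day, for example, 200 + 100 = 300 mg.

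**3. Drug described at Visit 5.** 14 days × 2 × 250 mg = 7,000 mg.

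**4. Drug left at Visit 6.** At adherence a, the remainder is 7,000 × (1 − a):

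| Adherence | Left at Visit 6 | Covers 1,000 mg? |
|---|---|---|
| 100% | 0 mg | no |
| 90% | 700 mg | no |
| 85.7% | 1,000 mg | just |
| 80% | 1,400 mg | yes |

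The break-even is a = 1 − 1,000/7,000 = 85.7%. Leftovers would cover the taper only for patients who had missed at least one dose in seven, and the return rule asks for those leftovers.

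**5. If the Visit 5 pack silently includes the taper.** The pack would hold 7,000 + 1,000 = 8,000 mg. This is an assumption, because neither pack size nor capsule strength is stated. It would be compatible with dispensing nothing at Visit 6. But the extra 1,000 mg would be unused drug at Visit 6, and the return rule would take it back unless that visit were exempt or the capsules were handed back after counting. The protocol says neither.

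**6. Effect on the calls.** Both calls take place in any case. With the taper, the last dose falls on about day 4 after Visit 6. Without it, the last dose is at Visit 6, the time since last dose at each call is about four days longer, and the Week 7 call no longer marks the end of a taper.

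**The case against.** The strongest reply is that this is missing detail, not a contradiction. The Visit 5 entry is a dose schedule, not a dispensed quantity. Drug beyond the four weeks is plainly planned, because the taper is listed in addition to them. The instruction given at Visit 6 presumes that patients have capsules in hand. The return sentence is garbled, and its purpose is to count capsules.

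Much of that stands. A reader might infer that the taper cannot be carried out at all; the documents do not support this, because an allowance issued at Visit 5 is possible. The reply does not remove the clash with the return rule, which applies at each visit and has no stated exception.

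Four further inferences are tempting and should not be drawn:

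- **That the taper length contradicts itself.** Four dosing days plus the day of reaching zero make the stated five.
- **That the calls are mistimed, or tied to an event that never happens.** The calls fall during Weeks 7 and 8. If Week 7 is read as days 43 to 49, it contains a taper end at day 46 or 47, and one week later (day 53 or 54) falls within days 50 to 56. The second call is tied to stopping study medication, which happens with or without a taper.
- **That adherent patients would fail the compliance rule.** Against an 8,000 mg pack, perfect adherence would read 7,000/8,000 = 87.5% and true 90% adherence 6,300/8,000 = 78.75%. But the protocol measures compliance against drug prescribed for the interval, not drug dispensed, so these figures are hypothetical.
- **That patients would be harmed, or that results would be mislabelled.** The documents describe no hazard of abrupt stopping, patients on placebo have no active drug to stop, and no planned analysis labels data as post-taper. Side effects are simply compared between arms by Fisher's exact test.

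**Conclusion.** The concern holds as an unreconciled conflict. The stated taper has no stated drug source, and the return rule has no exception that would let a patient keep any. Read literally, a fully adherent patient on 500 mg per day leaves Visit 6 with 0 of the roughly 1,000 mg needed. The gap concerns every patient who reaches Visit 6, up to about 45 per arm at the planned size.

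This rests on three assumptions: the patient is at 500 mg per day at Visit 6, the Visit 5 supply equals the dosing schedule, and the return rule covers unused capsules. If a taper allowance is packed at Visit 5, the supply gap closes but the return conflict remains.

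Severity is minor to moderate. The taper comes after the last visit at which the pain diary is scheduled, so the primary efficacy analysis, the intention-to-treat set and the power calculation are unaffected. The consequence is confined to conduct after Visit 6 and to the interpretation of the follow-up safety data.

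**What to change.** Reconcile Experimental Design and Dosing, the accountability list under Treatment Compliance, the dispensing row of Table 1, Study Timeline items 5 and 8, and the call descriptions in Adverse Events and Safety Evaluations, so that the dispensing, return and accountability rules are consistent with the taper the protocol states. The reconciled text should say at which visit the blinded taper supply is issued, and how that supply is treated in the Visit 6 return and capsule count. Add the date of last dose to the recorded data so that the two follow-up calls can be interpreted. The clinical content of the taper is for the sponsor to settle.

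The cost is a short protocol amendment, revised pharmacy and accountability instructions, and one additional data item. No extra patients or visits are needed.

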Neurosteroid quantification will be performed by highly sensitive and specific gas chromatography/mass spectrometry (GC/MS), preceded by high performance liquid chromatography (HPLC) purification as previously described ([name] et al. 2006a, [name] et al 2006b), with modifications. HPLC purification will be performed on an 1100 Series Agilent instrument. Standards and samples will be derivatized utilizing heptafluorobutyric acid anhydride (HFBA) and injected onto an Agilent 5973 mass spectrometer (MS) coupled to an Agilent 6890 N gas chromatograph (GC) equipped with an Agilent HP-5MS 30 m \times 0.250 mm \times 0.25 μ m capillary column. Positive ion electron impact (EI) ionization will be utilized in the GC/MS component. Serum samples will be analyzed in duplicate in positive ion electron impact mode (EI) using helium as the carrier gas. In addition to the GC/MS retention time characteristic of each neurosteroid, the definitive structural identification of each neurosteroid will be provided by its unique mass fragmentation pattern. Mass spectrometer single ion monitoring (SIM) will be used to focus on the most abundant ion fragment for each HFBA derivative (pregnenolone 298.2, allopregnanolone 496.2, pregnanolone 496.2, and androsterone 486.2). Only peaks with a signal to noise ratio greater or equal to 5:1 are integrated. The limit of neurosteroid quantification with this methodology is 2 picograms for pregnenolone, allopregnanolone, androsterone, and pregnanolone (femtomolar sensitivity). Intra-assay coefficients of variation continue to be very good utilizing this approach. For example, our last two serum sample investigations produced intra-assay coefficients of variation that were 1.8% and 1.6% for pregnenolone, 3.7% and 3.9% for allopregnanolone, 4.0% and 3.9% for androsterone, and 2.0% and 2.9 % for pregnenolone. These intra-assay coefficients of variation are in the same range as our prior investigations utilizing an EI approach.

Pharmacogenetics

We propose to conduct an exploratory analysis to assess the potential influence of genetic variations in enzymes involved in neurosteroid synthesis (P450scc, 3 β -HSD, 5 α -reductase, 3 α -HSD) on serum concentrations of neurosteroids and pregnenolone treatment response. Common variations in the genes coding for these enzymes (*CYP11A1*, *HSD3B1*, *HSD3B2*, *SRD5A1*) that influence enzyme activity have been identified (Pusalkar M 2009, Park et al 2007, Shimodaira et al 2010, Takahashi et al 2009).

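### Dose and draw times are not required at Visits 4–6, so exploratory analyses of on-drug neurosteroid levels carry avoidable timing noise

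*Combined protocol and SAP*

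**What the plan says.** **Sampling.** Study Timeline, item 6, provides that at Visits 1 to 6 "three extra red-top tubes will be collected for determination of pregnenolone levels and pregnenolone metabolite levels". The outcome section says the same in general terms: "Additional blood samples will be collected for serum analysis during all study visits". Neither gives a time of day or a time relative to dosing.

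**Dosing.** Study Timeline, item 4: "They will be asked to take the medication twice a day; once in the morning and once at night". Randomized drug is first dispensed at Visit 3 (Experimental Design: "Visit 3 (week 2, baseline visit): 50mg PO, BID x 1 week"), after the placebo lead-in. The draws at Visits 4, 5 and 6 therefore follow the 50, 150 and 250 mg twice-daily steps in the pregnenolone arm.

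**Dosing records.** Under Treatment Compliance: "Records will be kept of all drug dispensed to and returned by the subjects throughout the study". That is a count, not a time. The diary is described only as a pain score entered at bedtime.

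**Use of the levels.** The Pharmacogenetics section plans an exploratory analysis of whether enzyme gene variants influence "serum concentrations of neurosteroids and pregnenolone treatment response". It then mentions, as a prospect, serum biomarkers that might identify likely responders. The Statistical Methods section has no model for levels and no term for time since dose.

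**Pharmacokinetics.** The Pregnenolone paragraph says that "pharmacokinetic data for pregnenolone are limited". No half-life, peak time or peak-to-trough ratio is given.

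**The concern.** With twice-daily dosing, a level measured at a clinic visit depends on the patient and on how long ago the last capsule was taken. If that interval varies between patients and is unknown, it adds to the between-patient spread of levels, which is the quantity the exploratory analyses use. The consequence depends on the role of the level:

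- **Level as outcome (gene to level).** Timing noise unrelated to genotype leaves the genotype difference unbiased but widens its interval and lowers power.
- **Level as predictor (level to response).** The noise is measurement error in the predictor, so the slope is pulled toward zero and power falls as well.

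The second form matters to this group because its cited pilot evidence in mild TBI is a correlation between rises in serum levels and falls in symptom scores. A weak or absent association here could reflect the drug or the timing of the draw, and without the times nobody could tell which. Dose and draw times that are not captured at the visit cannot reliably be supplied later.

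**Working it through.** **1. The plan's own figure.** The only sample-size figure is 45 per group for the pain score (difference 0.6, SD 1.0, two-sided alpha 0.05, at least 80% power). The normal approximation gives 2 × (1.960 + 0.842)² / 0.6² = 43.6, so 44. The exact t calculation needs 45, with power 80.4%. The figure reproduces. It concerns pain scores only, and timing of blood draws does not enter it.

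**2. Inputs for the level analyses.** From the documents: 45 patients planned on pregnenolone, and on-drug draws at Visits 4, 5 and 6. Assumed, because the documents are silent: half-life h of 3, 6 or 12 h; between-patient CV of 50% or 80%; draw times uniform over a window; simple exponential decline.

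**3. Formulas (log scale).**
- Between-patient SD: B = √ln(1 + CV²), which is 0.472 for 50% and 0.703 for 80%.
- Timing SD: T = (ln 2 / h) × (window width / √12).
- Reliability: λ = B² / (B² + T²).
- A correlation is multiplied by √λ; a slope on log level as predictor is multiplied by λ.

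**4. One draw per patient.**

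| Window after dose | h | T | λ (CV 50%, 80%) | √λ (CV 50%, 80%) |
|---|---|---|---|---|
| 1–12 h | 3 h | 0.734 | 0.29, 0.48 | 0.54, 0.69 |
| 1–12 h | 6 h | 0.367 | 0.62, 0.79 | 0.79, 0.89 |
| 1–12 h | 12 h | 0.183 | 0.87, 0.94 | 0.93, 0.97 |
| 2–6 h | 3 h | 0.267 | 0.76, 0.87 | 0.87, 0.93 |
| 2–6 h | 6 h | 0.133 | 0.93, 0.96 | 0.96, 0.98 |
| 2–6 h | 12 h | 0.067 | 0.98, 0.99 | 0.99, 1.00 |

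Worst case in full: 0.2231 / (0.2231 + 0.5383) = 0.293, and √0.293 = 0.54. As information, 45 × λ runs from about 13 to 42 patients for the wide window.

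**5. What this means for power.** For an assumed true correlation of 0.40 and n = 45, power = Φ(atanh(r) × √42 − 1.96) = 78%. With r multiplied by 0.54 to 0.97 (0.216 to 0.387), it is 30% to 75%. With r multiplied by 0.87 to 1.0, it is 65% to 78%.

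**6. Two things that soften the result.**
- *Endogenous floor.* The Background says allopregnanolone rises more than five-fold on pregnenolone. Take a constant baseline of 1 and a mean on-drug level of 5, so level = 1 + A × 2^(−t/h). For h = 3 h over 1–12 h, the mean of 2^(−t/3) is 0.288, so A = 4 / 0.288 = 13.9. The level falls from 12.0 to 1.87, a 6.4-fold range, compared with 2^(11/3) = 12.7-fold without the floor. The timing SD becomes 0.546 (numerically), and the worst √λ rises from 0.54 to 0.65.
- *Three on-drug draws.* If draw times vary independently between visits and dose step is adjusted for, the timing variance is divided by 3. The worst √λ becomes √(0.2231 / (0.2231 + 0.1794)) = 0.74, or 0.83 with the floor as well. If a patient always attends at the same hour, this gain is smaller.

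**The case against.** The strongest reply is that little of consequence is touched. The affected work is exploratory in a trial that calls itself a pilot, the biomarker aim is a hope without a model, and the pilot correlation comes from another study. The gene analysis as worded is not confined to on-drug levels: everyone has draws at Visits 1–3 before randomized drug, and the placebo arm never has a drug peak or trough. Gene to treatment response needs no levels at all. No half-life, CV or draw window comes from the documents, and the benign window shows almost no loss. All of this stands, and it limits the point to a modest improvement.

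Some stronger readings are tempting but unsupported:

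- *That neither time is recorded.* The documents show only that the protocol does not require it. Case report forms and sample labels are not in the public documents.
- *That levels are a mixture of peak and trough.* No visit hours are given, and clinic appointments may cover only part of the dosing interval.
- *That gene effects on level are biased toward zero.* In that analysis level is the outcome, so precision is lost but the genotype difference is not distorted.
- *That the efficacy result is at risk.* The pain analysis uses diary scores.

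The reply does not remove the core. On-drug concentrations are within the scope of a stated analysis, and the protocol makes no provision for knowing when they were drawn relative to dose.

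**Conclusion.** The point holds as a cheap improvement to exploratory analyses. The protocol neither links the neurosteroid draw to the last dose nor asks for either time, and this adds noise to levels in the pregnenolone arm at Visits 4–6. Its size cannot be derived from the documents. Under the stated assumptions, the single-draw correlation factor is 0.54–0.97 for draws 1–12 h after a dose and 0.87–1.0 for draws 2–6 h after. With the floor and three independently timed draws, the worst case is about 0.83. A reader might infer a severe loss from the lower end, but that end needs a short half-life, an even spread over nearly the whole interval, no endogenous floor and a single draw, none of which the documents establish. The primary pain analysis, the sample size, and levels before randomized drug or in the placebo arm are not affected by time since active dose.

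**What to change.** At Visits 4, 5 and 6, in both arms so that the blind is kept, add two fields to the visit form: the date and clock time of the last study capsule, and the clock time of the neurosteroid draw. Visit 3 does not need them for this purpose, because it follows the placebo lead-in.

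In the statistics section, state that exploratory analyses of on-drug levels will use log concentration and include time since last dose and visit (which carries the dose step) as covariates, with all three on-drug visits used where possible. As pharmacokinetic data are limited, start with a linear term in time since dose and check its form against the data.

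Dosing, visits and sample size do not change. The cost is about a minute per visit and one or two extra model terms. The downside is reliance on the patient's recall of the last dose time, so some timing error will remain.
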